6.1.7. Vital Signs Measurements

Subjects' vital signs will be measured at Screening Day (performed 14 through 2 days prior to baseline) in order to ensure compliance with study inclusion criteria.

Vital signs measurements will include systolic and diastolic sitting position blood pressure, pulse rate, respiratory rate, and body oral temperature.

Additional vital signs measurements to assess subject's safety will be performed at baseline visit (Day 0) prior to drug injection, 2h ± 30min following drug injection, the following day (Day 1) after drug injection (24h ± 2h) and on study visits every 7 days thereafter, i.e., Day 7, Day 14, etc.

Additional pulse rate measurements to assess subject's safety will be performed at baseline visit (Day 0) prior to drug injection and 1h, 2h, 4h, 8h, 24h following injection in the opposite hand of blood sampling.

6.1.8. Serology Assays

Assays for HCV, HbSAg, and HIV will be conducted at Screening Day 1 (performed 14 through 2 days prior to baseline) in order to ensure compliance with study inclusion criteria.

6.1.9. Clinical Laboratory Tests

Clinical laboratory tests will be conducted at Screening Day (performed 14 through 2 days prior to baseline) in order to ensure compliance with study inclusion criteria. Additional studies will be conducted on different study visits according to schedule as written below. The maximum total blood volume will be 30 mL per visit. Every out-of-range value will be assessed by a physician and deemed as either clinically significant or clinically not significant. Values that represent a change from baseline in subject's medical status according to the laboratory normal ranges will be adequately documented as an AE as described in Section 9.

6.1.9.1. Hematology

Hematology tests will be conducted at Screening Day (performed 14 through 2 days prior to baseline) in order to ensure compliance with study inclusion criteria. Additional Hematology testing will be conducted to assess subject's safety on baseline visit prior to injections, at 24hr ± 2h following injection and on study visit Day 3, 7, 14 and 28.

Hematology tests will include Complete blood count (CBC) (including White blood cells [WBC] differential values) and coagulation tests: White blood cells (WBC), Red blood cells (RBC), Hemoglobin, Hematocrit, Mean corpuscular volume (MCV), Mean corpuscular hemoglobin (MCH), Mean corpuscular hemoglobin concentration (MCHC), Red cell distribution width (RDW), Platelets, Mean platelet volume (MPV), Fibrinogen, International normalized ratio (INR), Partial thromboplastin time (PTT) and Prothrombin time (PT).

6.1.9.2. Serum Chemistry Analysis

Testing of blood chemistry values will be conducted at Screening Day (performed 14 through 2 days prior to baseline) in order to ensure compliance with study inclusion criteria.

Additional Serum Chemistry testing will be conducted at Day 0 (before injection), 24hr ± 2hr following injection and on study visit Day 3, 7, 14 and 28.

Serum chemistry will include: Sodium, Calcium, Potassium, Phosphorus, Glucose, Liver enzymes (AST, ALT, Lactate dehydrogenase [LDH], Creatine-kinase MM [CK-MM], Gamma-glutamyltransferase [GGT], Alkaline phosphatase [ALP]), Bilirubin, Creatinine, BUN, Total protein, Albumin, Amylase, Creatine phosphokinase [CPK], C-reactive protein [CRP]).

In case of CK-MM >x5 ULN, subjects will undergo clinical assessment for symptoms and alternative causes, and renal function will be assessed (including urinalysis).

6.1.9.3. Urine Drug Screen

Urine drug screen will be conducted at Screening Day (performed 14 through 2 days prior to baseline) in order to ensure compliance with study exclusion criteria.

Drugs of abuse will include: amphetamines, barbiturates, benzodiazepines, cannabinoids, cocaine, alcohol, opiates, phencyclidine and propoxyphene.

6.1.9.4. Urinalysis

Urinalysis will be conducted at Screening Day (performed 14 through 2 days prior to baseline) in order to ensure compliance with study inclusion criteria and to allow differential diagnosis in case of urinary tract associated AE. Additional urinalysis testing will be conducted on study visit Day 14 and 28.

Urinalysis will include: Nitrite, Sodium, Potassium, Calcium, Phosphate, Protein, Red blood cells (RBC), WBC, Blood, Glucose, Ketone bodies, Bilirubin, Urobilirubin, Urine specific gravity, Osmolality, and pH.

6.1.10. ECG

Subjects' ECG will be performed at Screening Day (performed 14 through 2 days prior to baseline) in order to ensure compliance with study inclusion criteria. ECG is to be performed on at least a triplicate of heartbeats for all measurements and will be recorded at a speed of 25 mm/sec. Additional ECGs will be performed at 4h ± 30min, 8h ± 30min and 24h ± 2h following drug injection (Day 0-1) and on Days 14 and 28.

Computerized ECG analysis will include: Heart rate, Rhythm, PR interval, QRS axis, and QRS duration. The corrected QT interval and QTc will be calculated manually according to the Frederica formula. ECG will be recorded at a standard speed of 25 mm/sec and standard amplitude of 10 mm/mV.

6.1.11. Draize Score

Subjects' skin irritancy will be evaluated by Draize score at Screening Day (performed 14 through 2 days prior to baseline) in order to establish a baseline to compare following drug injection. For lipedema subjects evaluation of Draize score will be performed for each leg and for Dercum's disease subjects for each selected lipoma for injection.

Additional skin irritancy evaluation to assess subject's safety will be performed at baseline visit prior to injection, and on 2h ± 30min following injection, on the following day 24h ± 2h after drug injection and on study visits Day 7, 14, 21, 28 and 56.

Skin irritancy observations in the injected sites and contra-lateral sites will be scored using the Draize scale for scoring skin reaction:

Erythema and eschar formation		Edema formation	
No erythema	0	No edema	0
Very slight erythema (barely perceptible)	1	Very slight edema (barely perceptible)	1
Well defined erythema	2	Slight edema (edges are well defined by definite raising)	2
Moderate to severe erythema	3	Moderate edema (raised approximately 1mm)	3
Severe erythema (beet redness) to slight eschar formation (injuries in depth)	4	Severe edema (raised more than 1mm extending beyond area of exposure)	4

6.1.12. Photography of the Injected Site

Documentation of the skin condition and fat reduction effect in the injected area will be conducted at Screening Day (performed 14 through 2 days prior to baseline). Additional

photography will be performed at Day 1 (24h ± 2h following drug injection) and on study visits Day 7, 14, 21, 28 and 56.

Photography with a digital camera will include:

1. For Dercum's disease – Each of the injected site
 - a. A picture from above
 - b. A side picture

For each lipoma, the distance away from the lipoma with the best view of the skin will be recorded and fixed throughout the study to assess lipoma size changes.

2. For lipedema
 - a. Both sites above the knees
 - b. Sites of each knee separately
 - c. A side picture of each knee

Photography with a digital camera will be performed according to a detailed written manual.

6.1.13. Leg Circumference

Leg circumference measurement will be conducted at Screening (performed 14 through 2 days prior to baseline) to ensure compliance with study inclusion criteria and at Day 0 (before injection) to establish a baseline. Additional leg circumference measurements will be performed on Day 28 and 56.

The subject will be instructed to remove all garments from the legs and stand upright barefoot. The technician will stand on the subject's side and will palpate the knee area to locate the suprapatellar fat. If there is no excess to the suprapatellar fat measure 4-6 cm from the knee. With a cosmetic pencil, draw a horizontal line and record its distance from the floor. Extend the measuring tape around the leg. Position the tape in a horizontal plane at the level of the measurement mark. Check that the tape sits parallel to the floor and lies snug but does not compress the skin. Always position the zero end of the tape below the section containing the measurement value. Take the measurement in centimeters to the nearest 0.1 cm (one digit after the decimal point). The technician will take three measurements of leg circumference. When the measurement is measured the same twice (±0.5cm), that measurement will be used. If measurement are taken and all three are different, a fourth measurement will be taken until the same measurement is achieved twice.

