6.1.16.2. Evaluation of Secondary Endpoints

6.1.16.2.1. Local Fat Reduction for Lipedema Subjects

For lipedema subjects, local reduction in fat mass will be evaluated by measurement of the circumference of the leg above the knee. A local fat reduction is defined as a reduction (compared to baseline) in the circumference of the leg above the knee.

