6.2.2. Study Randomization

This is an open label study where all subjects will receive the investigational drug (RZL-012).

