10.5.5. Efficacy Analysis

Percent changes from baseline in local fat reduction (circumference of the leg above the knee, nodules size and/or numbers in the injected area) and tissue changes (fat thickness), will be presented in tabular form by visit.

Changes in nodular quality, local pain, quality of life and function will be presented in tabular form by visit and cohort.

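### Leg circumference: three readings are taken, but the recorded value is not defined; the mean of the three would be defined and more precise

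*Protocol*

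**What the plan says.** Protocol 6.1.13 sets out the measurement at a pencil line above the knee. The resolution is fine: "Take the measurement in centimeters to the nearest 0.1 cm". Replication is required: "The technician will take three measurements of leg circumference". The value to keep is then given by "When the measurement is measured the same twice (±0.5cm), that measurement will be used". If all three differ, "a fourth measurement will be taken until the same measurement is achieved twice". Measurements fall at Screening (for eligibility), Day 0 (baseline), Day 28 and Day 56.

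For lipedema subjects, section 6.1.16.2.1 makes this an efficacy measure: "A local fat reduction is defined as a reduction (compared to baseline) in the circumference of the leg above the knee". No minimum size of reduction is set. Protocol 10.5.5 and SAP 5.8.14 both plan a table of percent change from baseline by visit. Neither says how the value for a visit is derived from the readings. The SAP's list of lipedema tables has entries for additional measurements (14.3-5-8 to 14.3-5-10) but does not define their content.

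Protocol 6.2.2 states that the study is open label and that everyone receives RZL-012. No masked or independent measurer is described for circumference.

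**The concern.** At 0.1 cm resolution, two readings that count as the same can differ by up to 0.5 cm, which is 1% of a 50 cm leg. The phrase used for the recorded value therefore does not point to one number. It could be the first reading of the pair, the second, or their average. When more than one pair agrees, the pair is not fixed either.

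Two things follow. First, replication is paid for and then partly thrown away: at least one of the three readings plays no part in the value, and two play none if a single reading is kept. Second, an undefined value in an open-label cohort without a control arm can drift in the expected direction, and there is no comparison group in which the same drift would show. Circumference is part of the first-listed lipedema secondary endpoint and of the duration endpoint, in 6 subjects. The same rule also yields the screening value used for the 50 cm entry criterion.

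**Working it through.** **Inputs from the documents.** Three readings per leg and visit, 0.1 cm resolution, 0.5 cm agreement tolerance, repeats until two agree (6.1.13); a scale of about 50 cm (5.1, criterion 3). The documents give no reading error, effect size or power for circumference, so there is no stated figure to reproduce.

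**Assumption.** Single-reading error is normal and independent within a visit, with SD σ of 0.2, 0.3 or 0.5 cm (wider check: 0.1 to 1.0 cm).

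**Analytic anchor.** If σ is small enough that the tolerance never binds:
- one reading kept against the mean of three: variance ratio σ² / (σ²/3) = 3
- pair averaged against the mean of three: (σ²/2) / (σ²/3) = 1.5

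**Simulation with the tolerance applied.** 400,000 leg-visits per σ, readings rounded to 0.1 cm, first agreeing pair used, further readings if no two agree. The table gives the error SD of the recorded value in cm; ratios use unrounded SDs.

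| σ | Mean of three | One reading of the pair | Pair averaged | Variance ratio, one reading | Variance ratio, pair averaged |
|---|---|---|---|---|---|
| 0.2 | 0.117 | 0.194 | 0.149 | 2.75 | 1.62 |
| 0.3 | 0.174 | 0.271 | 0.231 | 2.44 | 1.77 |
| 0.5 | 0.289 | 0.420 | 0.393 | 2.11 | 1.84 |

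Over σ from 0.1 to 1.0 cm the ratios run from 3.0 down to 1.9 for one reading, and between 1.5 and 1.8 for the averaged pair. Reading the tolerance as a 1.0 cm window does not change the direction.

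**How often the rule leaves the value open.** At σ = 0.2, 0.3 and 0.5 cm, the eligible readings differ by at least 0.1 cm in about 97%, 95% and 93% of leg-visits. All three pairs agree in 87%, 60% and 28%.

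**Bound on selective recording.** The mean distance from highest to lowest eligible reading is 0.32, 0.38 and 0.36 cm. Recording the highest at baseline and the lowest later would, with no true change, give a mean apparent reduction of that size: 0.32/50 = 0.6% to 0.38/50 = 0.8%. This is a limit, not an expected bias; a random pick within the pair gives none.

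**What carries through to change from baseline.** Let e be the within-visit error SD and b an assumed per-visit SD for re-placing the line and other between-visit variation. With two independent visits, SD(change) = √[2(e² + b²)]. At σ = 0.3 cm, comparing e = 0.271 (one reading) with e = 0.174 (mean of three):
- b = 0: 0.38 against 0.25 cm, 36% lower
- b = 0.3: 0.57 against 0.49 cm, 14% lower
- b = 0.5: 0.80 against 0.75 cm, 7% lower
- b = 1.0: 1.47 against 1.44 cm, 2% lower

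Starting instead from the averaged pair (e = 0.231), the reductions are 25%, 8%, 4% and 1%.

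**The case against.** A reader might infer that the protocol lets an unblinded technician choose the value. It does not say so: it is silent on which agreeing reading counts, and a site could settle on the first reading or the pair mean and apply that consistently. That the measurer knows visit and treatment follows from the open-label design; that anyone would steer the value does not.

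A reader might also infer that a choice within a pair could create or hide the endpoint. Any reduction does count as fat reduction under 6.1.16.2.1, but the planned output is a descriptive percent-change table. No circumference responder rate, success threshold or confirmatory test is stated. The same endpoint item also includes ultrasound, and no hierarchy is set.

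Three further points have force. If the pair is averaged, the loss is smaller than if one reading is kept. The readings at a visit share one line, found by palpation or set 4 to 6 cm from the knee, so averaging cannot reduce the error of finding that line again. And the two-agree rule does screen out a gross misreading, which a plain mean of three does not.

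These points limit the size of the problem. They do not remove it: the recorded value remains undefined, and the mean of three has the lower error variance under each reading of the rule examined, for independent reading error without gross misreadings.

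**Conclusion.** The point holds as a gap in definition with an avoidable loss of precision. The analysis value for circumference is not unique under 6.1.13, and the SAP does not repair this. For σ of 0.2 to 0.5 cm, within-visit error variance is about 2.1 to 2.8 times that of the mean of three if one reading is kept, and about 1.6 to 1.8 times if the pair is averaged. The direction does not depend on σ over 0.1 to 1.0 cm; the sizes in cm do, and σ is assumed.

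The gain in precision of change from baseline is smaller and cannot be fixed from the documents, because they give neither the reading error nor the between-visit component. It may be only a few percent if re-placing the line dominates. The room for selective recording is real but modest, at most about 0.8% of 50 cm on average for these SDs under the 0.5 cm tolerance, and nothing in the documents shows that it would be used. The primary safety endpoint and the sample size do not depend on circumference. The change is worth making because it is nearly free.

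**What to change.** In protocol 6.1.13, and again in the SAP beside 5.8.14:
- Record every reading in the CRF.
- Define the analysis value as the mean of the three readings.
- If no two of the three agree within 0.5 cm, take the fourth reading already foreseen and use the median of all readings taken. In the simulation this arises in under 1% of leg-visits at σ = 0.3 cm and about 7% at σ = 0.5 cm.
- Apply the same rule to each leg at Screening, Day 0, Day 28 and Day 56.

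With every reading on file, a third reading far from the other two can be queried, which answers the concern about gross misreadings.

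Cost: one or two sentences in each document, and CRF fields for the individual readings if they are not there already (the CRF is not among the documents). The three readings are already required, so there is no new visit, procedure or subject burden.

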6.1.14. Imaging: Ultrasound (US)

Evaluation of Ultrasound (Vevo 2100 or 3100 with transducers at 20, 50 or 70 mHz; or Esaote MyLab Gamma Ultrasound System with 20 mHz transducer) will be conducted at Screening

(performed 14 through 2 days prior to baseline) to ensure compliance with study inclusion criteria and establishing a baseline. For Dercum's disease subjects - nodule size and quality will be assessed, for lipedema subjects – nodular size (if applicable), nodular quality and fat thickness will be assessed. Additional US will be performed on Day 28 and 56.

Nodular quality for Dercum's subjects will be assessed according to the following parameters: capsule visibility, hyperechoic or hypoechoic tissue, reverse starry sky (small black dots all over consistent with angioliipoma), flurry or snowstorm appearance, location measured to the skin and vascularity internal or around the lipoma.

[figure not shown]
Nodular quality for lipedema subjects will be assessed according to the following parameters: hyperechoic or hyperechoic tissue, flurry or snowstorm, internal hypoechoic rounded area consistent with a vessel and distance from skin.

Additional ultrasound imaging will be conducted at Day 0 (before injection):

- For Dercum's disease subjects - nodule size evaluation to ensure proper dose injection. The selected nodules for injection will be marked in circles with a non-erasable pen. This mark should be strengthened on every visit.

Assessment of nodular size will be by diameter (mm) and surface (mm²) in three dimensions as illustrated below:

- Height
- Width
- Length

- **Height**
- **Width**
- **Length**

- For lipedema subjects – assessment of presence of nodules to be injected along the horizontal plane 4-6 cm in the suprapatellar fat. The selected nodules for injection will be marked in circles with a non-erasable pen. This mark should be strengthened on every visit. If no nodules are noted in the horizontal plane, drug will be injected in to the fatty tissue and in this case small nodules seen in ultrasound will be followed for changes.

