	
1. Hematology: Complete blood count (CBC) including White blood cell [WBC] differential values, Fibrinogen, and coagulation (International normalized ratio [INR], Partial thromboplastin time [PTT] and Prothrombin time [PT]).2. Serum chemistry analysis: sodium, calcium, potassium, phosphorus, glucose, liver enzymes (Aspartate aminotransferase [AST], Alanine aminotransferase [ALT], Lactate dehydrogenase [LDH], Creatine-kinase MM [CK-MM], Gamma-glutamyltransferase [GTPP], Alkaline phosphatase [ALP]), Bilirubin, Creatinine, Blood urea nitrogen [BUN], Total protein, Albumin, Amylase, Creatine phosphokinase [CPK], C-reactive protein [CRP]).3. Urinalysis: Nitrite, Sodium, Potassium, Calcium, Phosphate, Protein, Red blood cells (RBC), WBC, Blood, Glucose, Ketone bodies, Bilirubin, Urobilirubin, Urine specific gravity, Osmolality, and pH. 
- In addition, photography and evaluation of skin irritancy by Draize score of the injection site area.- For Dercum's disease subjects – ultrasound assessing nodules size (diameter) and quality. Determining which nodules are to be injected with a total of 40mg RZL-012.- For lipedema subjects – measurement of leg circumference above the knee and assessing fat thickness and nodular quality by ultrasound.- For lipedema subjects - QOL and function questionnaires. 
Baseline visit (Day 0):
 
- Pre-treatment: eligibility confirmation, vital signs, Draize score, leg circumference, clinical evaluation of local pain and tenderness to pressure and nodules size and/or numbers, blood sample for serum chemistry, and hematology baseline level will be taken.- Treatment - All injections will be administered 45 ° to the skin surface using a 1 mL Luer-lock syringe and a 30 G x 1/2" needle (the hole of the needle pointing into the fat layer).- Post treatment: ECG (4h and 8h ± 30min post injection), pulse rate (1h, 2h, 4h, 8h, 24h post injection in the opposite hand of blood sampling), vital signs (2h ± 30 min post injection), Draize score (2h post injection ± 30 min), adverse events (AEs) will be recorded. 
Schedule visits (Day 1-28):
 
- Day 1 following treatment will include: ECG, vital signs including pulse rate, Draize score, and photographs of the treated area, clinical evaluation of local pain and tenderness to pressure. Subjects will start applying an anti-histamine gel.- For safety reasons 24hr ± 2hr following injection, Blood samples for serum chemistry and hematology will be taken- Day 3 following treatment will include Serum chemistry and hematology.- Visits will take place every 7 days ± 1d from treatment till Day 28. During visits, all tests (physical exam, vital signs, ECG, clinical laboratory tests, urinalysis, Draize score, leg circumference above the knee, weight measurement, QOL and function questionnaires in lipedema subjects, clinical evaluation of local pain and tenderness to pressure and reduction in nodules size and/or numbers, photographs and ultrasound will be performed according to schedule (Table 2).- Subjects will be questioned for AEs every visit.- Subjects will record their daily use of analgesics. Diaries will be checked and data will be captured in the CRFs. 
Follow-up visit (Day 56):
 
- Subjects will be followed on Day 56 following injection.- A week before Day 56 visit, subjects will record their daily use of analgesics. Diaries will be checked and data will be captured in the CRFs.- Evaluation of the injected area will be performed by Draize score, photographs, QOL and function questionnaires in lipedema subjects, clinical evaluation of local pain and tenderness to pressure and reduction in nodules size and/or numbers.

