6.1.16.2.3. Duration of the fat reduction effect

The duration of the local fat reduction in all subjects will be evaluated by ultrasound and by leg circumference above the knee in lipedema subjects at Day 56 compared to baseline and to Day 28.

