6.2.3. Study Treatment

6.2.3.1. Treatment with RZL-012 Investigational Therapy

[figure not shown]
RZL-012 is an investigational product supplied as a single dose single treatment injection in multiple sites (2-16) of injections. Before injection, subjects will be advised to keep their regular diet and physical activity.

The injection dosing regimen and technique is crucial for the therapy safety and efficacy. Syringes will be filled with 0.1 mL RZL-012 and the number of syringes will be compatible with the number of injections. All injections will be administered diagonally in 45 °, using a 1 mL Luer-lock syringe and a 30 G x 1/2" needle.

The hole of the needle should be pointing into the fat layer and the injection direction should be towards earth. An attempt to pull the plunger should be made before injecting to ensure that no blood is coming out. If so, the plunger should be pushed down to inject the medicine. The formulation is viscose, therefore resistance is expected while injecting.

[figure not shown]
For Dercum's disease - The 1st cohort will be comprised of subjects with Dercum's disease. Subjects will receive a single treatment in multiple sites (2-8) according to the design below (Figure 2).

Figure 1: RZL-012 Injection Design in Dercum's Disease Subjects

Injections will be diagonally (45°) to the skin surface towards the center of the nodule and the distance between injections in a nodule will be 1 cm (Figure 2).

Figure 2: RZL-012 Injection Sites in Dercum's Disease Subjects

For Lipedema - The 2nd cohort will be comprised of subjects with lipedema with substantial fat above the knee. A grid line will be drawn with a makeup pencil in a horizontal plane (Figure 3) 4-6 cm from the suprapatellar fat and its distance from the floor recorded. An attempt should be made to find palpable nodules along the grid line. The injection sites will be marked in circles with a non-erasable pen. This mark should be intensified upon following visits. Injections will be given in multiple sites (4-8 in each leg), diagonally (45°) to palpable nodules, in the fat above the knee. An attempt should be made to lift the nodule and inject into the middle of the fat-mass. If no nodules are noted in the horizontal plane, drug will be injected into the fatty tissue (in this case small nodules seen in ultrasound will be followed for changes). Injections will be on the same horizontal plane.

Figure 3: RZL-012 Injection in Lipedema

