6.2.4. Baseline Visit

Baseline visit is defined in the study as Day 0. Baseline visit will be performed to complete screening evaluation, and to review all procedures necessary to confirm subject eligibility. Subjects will stay under supervision in the study center till 8h + 3h following drug injection.

Screening information may be considered for baseline data if acquired within the adequate timeframe as described in Table 2.

Table 2: Subject Information and Timeframes

Information	Timeframe	Follow-up Timeframe
Informed Consent Form	Signed prior to any study dedicated procedure	
Medical History and Concomitant Medications	At Screening Day visit	
Physical examination	At Screening Day visit and at Day 28	
Pain Measurement	At Screening Day visit and at Days 14, 28	At Day 56
QOL Measurement in lipedema subjects	At Screening Day visit and at Days 14, 28	At Day 56
Vital Signs	At Screening Day visit and at Days 0 (pre and following injection), 1, 7, 14, 21, 28	
Pulse rate	At Day 0 (following injection) and at Day 1	
ECG	At screening Day 1 visit, at Day 0 (following injection) and at Days 1, 14, 28	
Draize Score at the Injected Site	At Screening Day and at Days 0 (pre- and following injection), 1, 7, 14, 21, 28	At Day 56
Serology assays (HbSAg, HCV and HIV)	At Screening Day visit	
Drug screen	At Screening Day visit	
Serum chemistry and Hematology	At Screening Day and at Day 1, 3, 7, 14 and 28	
Urinalysis	At Screening Day visit and at Days 14 and 28	

Information	Timeframe	Follow-up Timeframe
Ultrasound for nodules quality and size. Fat thickness – for lipedema	At Screening Day visit and at Day 28	At Day 56
Ultrasound for nodules size and selection for injection	At Days 0 (pre- injection)	
Photography of the Injected Sites	At Screening Day visit and at Days 1, 7, 14, 21, 28	At Day 56
AE Assessment	At Days 1, 3, 7, 14, 21, 28	At Day 56

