#### 14.3 Efficacy Assessment

Table 14.3-1 Pain by comparative scale by cohort

Table 14.3-2 Reduction in Pain from baseline by visit

Table 14.3-3 Relative Change in local pain

14.3-4 Dercum's disease cohort

Table 14.3-4-1 Number of Lipomas by visit

Table 14.3-4-2 Reduction of number of Lipomas from baseline by visit

Table 14.3-4-3 Relative Change in Number of lipomas

Table 14.3-4-4 Size of lipomas by visit and type

	DOCUMENT NUMBER: 050-BST-PLN-001	PAGE: 21 of 24
TITLE: Statistical Analysis Plan of Protocol Number RZL-012-FD-P2aUS-001		EFFECTIVE DATE : 02/05/2019 REVISION NUMBER : 1.0

Table 14.3-4-5 Reduction\*\* in Size of lipomas by visit and type

Table 14.3-4-6 Relative change in Size of lipomas by visit and type

Table 14.3-4-7 Lipoma description

14.3-4.8 Correlation between pain and size of lipomas

Table 14.3-4.8-1 Correlation between lipoma size and pain for lipomas with Fibrotic tissue not associated with the capsule

Table 14.3-4.8-2 Correlation between lipoma size and pain for lipomas with Fibrotic tissue associated with the capsule

Table 14.3-4.8-3 Correlation between reduction in lipoma size and reduction in pain for all lipomas

14.3-5 Lipedema cohort

Table 14.3-5-1 Number of fat locations by visit

Table 14.3-5-2 Thickness of fat locations by visit for right/left leg

Table 14.3-5-3 Reduction\*\* in fat locations Thickness by visit and type

Table 14.3-5-4 Relative change in fat locations Thickness by visit and type

Table 14.3-5-5 Fat tissue description

Table 14.3-5-6 Nodule description

Table 14.3-5.7 Correlation between reduction in nodule size and reduction in pain

Table 14.3-5-8 Additional measurements

Table 14.3-5-9 Reduction\*\* in additional measurements

Table 14.3-5-10 Relative change in additional measurements

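### In the lipedema cohort, ultrasound fat thickness and nodular quality have no baseline at the injected sites, and no method is stated for returning the probe to those sites at Day 28 and Day 56

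*Protocol*

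**What the plan says.** - **Timing of the outcome scans.** Protocol 6.1.14 and Table 2 (6.2.4) place lipedema fat thickness and nodular quality at Screening, and then "Additional US will be performed on Day 28 and 56".
- **The Day 0 scan.** Its row in Table 2 reads "Ultrasound for nodules size and selection for injection". For lipedema, 6.1.14 describes it as a check for nodules to inject along the injection line; thickness and quality are not mentioned.
- **Marking.** At that Day 0 scan, "The selected nodules for injection will be marked in circles with a non-erasable pen. This mark should be strengthened on every visit". Section 6.2.3.1 likewise has the injection sites circled and the ink renewed at later visits. If no nodule lies on the line, fat is injected and small nodules seen on ultrasound are followed; no marking of those nodules is stated.
- **Line height.** The injection line is drawn "4-6 cm from the suprapatellar fat and its distance from the floor recorded" (6.2.3.1).
- **Visits.** "Visits will take place every 7 days ± 1d from treatment till Day 28" (synopsis, Visit Schedule); the only later visit is Day 56. Duration of effect is judged "at Day 56 compared to baseline and to Day 28" (6.1.16.2.3).
- **Baseline rule.** Protocol 10.5.3 and SAP 5.8.11 take the last evaluable value before injection.
- **Reporting.** The SAP table shells include "Table 14.3-5-2 Thickness of fat locations by visit for right/left leg", followed by tables of reduction and relative change in thickness. Listing 16.2.5-3-1 counts injected fat locations.

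**The concern.** The SAP treats a fat location as something that can be followed from visit to visit. That requires the pre-injection and post-injection readings to come from the same place. In lipedema the pre-injection thickness and quality readings are made before the places are chosen, and nothing ties the Screening probe position to the sites injected later. Sites are then sought where nodules can be felt, so they may differ systematically from wherever the Screening reading was taken.

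The later scans depend on finding the sites again. No passage says how this is done if a circle is no longer legible, and the longest interval without renewal falls immediately before the scan that supports the duration endpoint.

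At stake are the ultrasound tissue-change endpoint in lipedema (6.1.16.2.4) and the ultrasound part of the duration endpoint. Nodular quality is descriptive (echogenicity, texture, depth), so reading a different spot can appear as a change of category.

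**Working it through.** The plan states no figure for relocation error, so the check sets the schedule side by side and adds simple date and spacing arithmetic.

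**1. What is measured when** (Protocol 6.1.12, 6.1.13, 6.1.14, 6.2.3.1, Table 2)

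| Item | Screening | Day 0, before injection | Day 28 | Day 56 |
|---|---|---|---|---|
| Lipedema fat thickness | yes | not stated | yes | yes |
| Lipedema nodular quality | yes | not stated | yes | yes |
| Lipedema nodule size | if applicable | possibly (Table 2 row is not limited to one cohort) | yes | yes |
| Lipedema sites circled | not yet chosen | yes | renewed | renewed |
| Leg circumference, with line height | yes | yes | yes | yes |
| Photographs | yes | no | yes | yes |
| Dercum's nodule size | yes | yes, and marked | yes | yes |

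Under the last-value rule, the baseline for the first two rows is the Screening value.

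**2. Age of that baseline.** Screening runs from Day -14 to Day -2.
- To marking: 2 to 14 days.
- To the Day 28 scan: 28 + 2 = 30 to 28 + 14 = 42 days.
- To the Day 56 scan: 56 + 2 = 58 to 56 + 14 = 70 days.

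These are nominal. Ultrasound is not on the rescreening list in 6.2.1, so the scan could be older in a rescreened subject.

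**3. Renewal of the marks.** Visits on Days 0, 1, 3, 7, 14, 21, 28 and 56 give gaps of 1, 2, 4, 7, 7, 7 and 28 days. With windows of ±1 day the last gap is (56 - 1) - (28 + 1) = 26 to (56 + 1) - (28 - 1) = 30 days. If the synopsis window for Day 56 is read as up to 3 days, it is 24 to 32 days.

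**4. Position along the line.** All sites on a leg share one horizontal line, so line height gives the level only. Section 6.2.3.1 sets minimum spacings of 3 cm (12 injections, 6 per leg) and 2 cm (16 injections, 8 per leg).
- Minimum span per leg: (6 - 1) × 3 = 15 cm, or (8 - 1) × 2 = 14 cm.
- Shift that puts the probe midway between sites at minimum spacing: 3/2 = 1.5 cm, or 2/2 = 1.0 cm.
- Opposite extreme, assuming even spread around the full 50 cm of the inclusion criterion: spacing 50/6 = 8.3 cm or 50/8 = 6.25 cm, so midway is about 4.2 cm or 3.1 cm.

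**5. What a reported change contains.** Let s be the injected site, x the point read at Screening, and s' the point read at Day 56. Then

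reported change = [T56(s') - T56(s)] + [T56(s) - T0(s)] + [T0(s) - Tscr(x)].

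Only the middle term is change at the injected site. The last term (place and time) affects both Day 28 and Day 56 through the baseline. The first is relocation error at Day 56; a corresponding term applies at Day 28. Both legs are injected and there is no control arm, so the design offers no estimate of either unwanted term. The documents give no between-location variability, so their size in millimetres cannot be calculated.

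**6. Number of sites.** The synopsis, 3.2, the 3.3.1 text, 8.4.2 and the SAP describe 3+3: 3 × 12 + 3 × 16 = 84. Section 6.2.3.1 describes 2/2/2: 2 × 8 + 2 × 12 + 2 × 16 = 72. Those dosing passages conflict and must be reconciled separately.

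**The case against.** The strongest reply is that the pen mark is not the only locator. Line height is recorded at injection and with each circumference measurement. The sites are photographed on Days 1, 7, 14, 21, 28 and 56 under a written manual, so a photograph with freshly renewed marks can exist at Day 28. The endpoints refer to a region or area rather than a point. Injections are to be spread as widely as possible, so the minimum spacings are a worst case. The photography manual, the CRF fields and the injection-site figures are not available to us and may hold positional detail. Efficacy is secondary and mainly descriptive in this small, uncontrolled study.

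Much of this stands, and it rules out several stronger inferences:

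- **That sites are found again only by ink, or that the scans share no coordinate.** Line height and photographs contradict this. What is not stated is a position along the line.
- **That the marks will be lost by Day 56.** No document gives the durability of the pen; the text shows only an interval without scheduled renewal.
- **That Dercum's subjects are equally affected.** Their nodules are discrete, at least 2 cm across, chosen at Screening, and re-measured and marked on Day 0.
- **That circumference is compromised.** It has its own Day 0 baseline and needs no site mark.
- **That up to 6 × 16 = 96 sites are involved.** Neither dosing description gives every subject 16 injections.
- **That a probe midway between sites reads untreated tissue.** No radius of effect is given.

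The reply does not answer the main point. No photograph, manual or line height can place the Screening scan at sites that had not yet been chosen. Nor does any passage say that height or photographs are to guide the probe. A fixed camera distance is specified only for lipomas, and no Day 0 photograph is scheduled.

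**Conclusion.** The point holds for lipedema fat thickness and nodular quality. As scheduled, their baseline is not tied to the injected sites, although the SAP reports thickness change by location. This follows from the order of events and does not depend on whether ink fades. The second part, relocation at Day 28 and Day 56, is a risk rather than a demonstrated failure. It is greatest at Day 56, after a nominal 28 days without scheduled renewal, against at most 7 days before.

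Its extent is six subjects and 84 or 72 sites, depending on which dosing text applies. The effect on the estimates cannot be quantified from the documents, and its direction is unknown. The conclusion assumes that the Day 0 lipedema scan records no more than 6.1.14 and Table 2 state, and that no unseen manual prescribes site-by-site relocation. The primary safety endpoint is unaffected. The change should be made because it is cheap and the data cannot be recovered after injection.

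**What to change.** 1. In 6.1.14, Table 2 and the schedules (Protocol Appendix I, SAP 5.4.2), add lipedema fat thickness and nodular quality at each marked site to the Day 0 pre-injection scan. The existing last-value rule then makes these the baseline. Keep the Screening scan for eligibility.
2. On Day 0, record for each site its tape distance along the grid line from a fixed landmark, such as the patellar midline, together with the line height already recorded. Do the same for any small nodules followed because none lay on the line.
3. State in 6.1.14 that this record and the photographs guide probe placement at Day 28 and Day 56, and carry the site identifier into the SAP location tables.

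This needs no new visit, scan session or staff: a one-page map and a slightly longer Day 0 visit for six subjects. If any lipedema subject has already been injected without these readings, the report should say that the thickness and quality baseline was not site-specific.
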